21. POTENTIAL BENEFITS TO PARTICIPANTS

Potential benefits of the study are linked to the goal of the project – providing access to an alternative method for cervical cancer screening through self-collection for HPV testing. In addition, all participants will benefit by participating and attending cervical cancer workshops in their native language, led, and sponsored by a trusted community organization. This research has the potential to reduce barriers to screening for vulnerable

populations such as immigrant and refugee women or other women who do not feel comfortable with clinician-collection for screening.

22. RISKS TO PARTICIPANTS

This protocol is considered to have a minimal risk to participants. Potential risks of the both collection methods (clinician-collected and self-collection) are mild physical discomfort, pain and temporary increase in vaginal spotting lasting 1 - 2 days. Risks will be minimized by explicit translated instructions on how to use the device. Additional risk of undetected cervical dysplasia is dependent on screening test sensitivity.

This research protocol does subject participants to increased risk of false negative screening tests than usual standard of care. Self-collection has a small increase in false negatives compared to clinician collection due sample errors. In a study by Tranberg et al., concordance for HPV detection between self-collected samples and clinician-collected samples shows 89% agreement (81% sensitivity, 92% specificity), which is an acceptable concordance to justifying offering self-collection to participants in this study.²⁰

23. PROVISIONS TO MONITOR THE DATA TO ENSURE THE SAFETY OF THE PARTICIPANTS

The Principal Investigators (Drs. [name] and [name]) will be responsible for reviewing and monitoring all study data and any adverse events. The Principal Investigator will meet with study personnel at least monthly to evaluate study progress, including periodic assessments of data quality and timeliness, participant recruitment, accrual and retention, participant risk versus benefit, and other factors that can affect study outcomes. All unanticipated problems and adverse events that require reporting to the IRB will be reported to the University of Wisconsin Madison (UW) Health Sciences-IRB (HS-IRB).

24. ECONOMIC BURDEN TO PARTICIPANTS

Potential costs to participants is travel to and from the community center.

25. RESOURCES AVAILABLE

Will the research be conducted outside School of Medicine and Public Health or UW Hospitals and Clinics (e.g. the researcher does not have an SMPH research feasibility attestation for this study)?	 YES (complete 25.1)  NO (remove text below, but retain this section)
--	---

Feasibility of recruiting:

- Estimates of Hmong, Karen, and Burmese and Karen women in the Milwaukee area was calculated by using published data from 2019 by the Pew Research Center and population estimate of 50.52% in the US population are women.
- Number of Hmong women in the Milwaukee area age 30 to 64 is approximately 2001.
- Number of Burmese women in the Milwaukee area age 30 to 64 is approximately 1273.
- Estimate recruitment will be 80 Hmong, 48 Karen, 48 Burmese and 64 Karen women participants
- These are not true estimates of the number of women in the population we are recruiting from due to age and specific ethnicity. Inclusion of women in this study is between age 25-65 and Hmong, Karen, Burmese or Karen. Karen and Karen is a smaller ethnic group commonly grouped together with other ethnic groups categorized in the general Burmese ethnic group.
- Potential participants the research team has access to is not yet determined, although MCHH routinely recruits for and conducts educational workshops in which 368 participants were recruited between July 1, 2020 and June 30, 2021.
- Additional resources and networks will be provided through collaboration with the City of Milwaukee Health Department.

Personnel:

- All personnel who will engage in the study will have appropriate experience, credentials, and training.
- All personnel will have sufficient time available to conduct the research:
 - o Primary Investigator [name] will commit 5% of FTE to the research project.
 - o Collaborators [name] and [name] will commit 20% of FTE each to the research.
- All personnel will perform study activities commensurate with their job description and scope of practice and will be appropriately supervised and monitored.

Space and Facilities:

- Appropriate approvals and safeguards are/will be in place for both clinical and non-clinical space and facilities where study activities may occur. Type and risk-level of procedures have been accounted for when selecting space and facilities.
- Location of research activities will be at MCHH's community center with adequate space to conduct workshops activities as well as post-workshop cervical cancer screening.

Availability of medical or psychological resources:

- There will be a medical professional on site for support during and after workshop activities.
- There will be referral to primary care clinicians or other community providers for support of any additional medical or psychological needs as a result of this research study. Anticipated psychological need will be minimal. More than minimal medical need is anticipated for follow-up of abnormal results, this is anticipated and addressed in the protocol.

26. MULTI-SITE RESEARCH

NA

<https://doi.org/10.1186/s12879-018-3254-y>

28. APPENDICES**APPENDIX A: Milwaukee Consortium for Hmong Health Cervical Cancer Workshop Intake Form**

Participant Intake Form Cervical Cancer

Office Use:
ID# _____
CHW: _____
Grant: _____
Date: _____

Personal Information:

First Name: _____ Middle Initial: _____ Last Name: _____
 Phone Number: _____ Cell or Landline (circle one) Email: _____
 Address: _____ Apt./Unit #: _____
 City: _____ State: _____ Zip Code: _____
 Date of Birth: _____ / _____ / _____ Gender: Male Female Ethnicity: _____

Medical History:

Month and year of previous Pap test:

_____ / _____ (mm/yyyy) Never Unknown

Do you need help getting a Pap test? Yes No

What type of insurance do you have? Private Medicaid Medicare None

Other: _____

Who is your primary doctor? _____ Primary Care Location: _____

What reasons may be stopping you from getting a Pap test?

 No symptoms	 I'm too busy/No time	 No family history of cervical cancer
 No transportation	 I am afraid it will hurt	 My doctor never mentioned it
 Too expensive/No Insurance	 I don't want to know the results	 Embarrassed
 I don't know where to go	 Childcare	 Long wait to get an appointment
 Spouse will not allow it		 None

[figure not shown]
Participant Evaluation

After today's workshop, how likely are you to...?					
	Not likely		Neutral		Very Likely
1. Receive a Pap/Pelvic exam this year or as recommended?	1	2	3	4	5
2. Spread the word about the screenings available to your family members?	1	2	3	4	5
3. To encourage your family members to get screened?	1	2	3	4	5
4. Practice healthy behaviours that can reduce your risks for cervical cancer?	1	2	3	4	5

Other comments/questions about Cervical health:

Revised: 7/2019

APPENDIX B: Evalyn® Brush (Rovers® Medical Devices, Netherlands) and Instructions

Wash your hands before usage.

Remove the Evalyn Brush from the packaging. Do not throw the packaging away, as it is necessary for sending the Evalyn Brush to the laboratory after usage.

Press the sides of the pink cap with your thumb and index finger to remove the pink cap from the Evalyn Brush. Ensure that you do not touch the white fibres of the Evalyn Brush with your hands!

Obtain the sample whilst in a standing position. Assume a comfortable stance (e.g. as if you were about to insert a tampon).

[figure not shown]
Spread your labia with one hand, and with the other, insert the Evalyn Brush into your vagina until the wings touch your labia.

Hold the transparent casing with one hand, and with your other hand, push the pink plunger in the direction of the transparent casing. You will hear and feel a click when the brush is in the right position with the pink plunger directly against the casing.

Turn the pink plunger five rotations in the same direction. After each rotation, you will hear a click. This helps you count the rotations. After turning the plunger five times, carefully remove the Evalyn Brush.

Hold the transparent casing with one hand, and with your other hand, pull on the pink plunger until the white brush disappears into the casing. When doing so, do not touch the top part of the Evalyn Brush above the wings.

Hold the transparent end to ensure the white brush does not extend again. Place the pink cap back on the Evalyn Brush using your thumb and index finger. You will hear a click when it is properly in place.

Put the Evalyn Brush back inside the packaging.

Place the packaging containing the Evalyn Brush into the plastic bag provided and seal it.

Use the return envelope to send the plastic bag containing the Evalyn Brush together with other required information.

APPENDIX C: UW Health Researchers Post-Workshop Satisfaction Survey (UW-PSS)

Due to the number of skip logics, the survey is best viewed through Qualtrics

Link: https://uwmadison.co1.qualtrics.com/jfe/form/SV_bQT22KcJ9g7Qklw

Community Health Outreach to Increase Cervical Cancer Education and Self-Collection Screening (CHOICES) Program among Burmese and Hmong Women in Wisconsin.

This post-workshop participant survey is designed to be filled out with the guidance of Community Health Workers.

Please do not have the participant fill this information on their own.

Please copy the below information from the paper MCHH intake form:

Section A

After today's workshop, how likely are you to....?

	Not Likely	Somewhat unlikely	Neutral	Somewhat likely	Very Likely
1) Receive a Pap/Pelvic exam this year or as recommended?					
2) Spread the word about the screenings available to your family members?					
3) To encourage your family members to get screened?					
4) Practice healthy behaviors that can reduce your risks of cervical cancer?					

What workshop did the participant attend?

Clinician-collection education → Continues to Section B

Self-collection education → Skip to Section D

Section B

Did the participant get screening for cervical cancer today? (Clinician Collected)

Yes

No → Skip to Section C

Section B (continued)

How comfortable did you feel with this method?

- Extremely comfortable
- Somewhat comfortable
- Neither comfortable nor uncomfortable
- Somewhat uncomfortable
- Extremely uncomfortable

How likely would you get screening for cervical cancer again?

- Extremely likely
- Somewhat likely
- Neither likely nor unlikely
- Somewhat unlikely
- Extremely unlikely

In the workshop you attended today, we did not discuss self-collection as an option.

If self-collection was an option, would you have preferred this method?

- Yes
- Maybe
- No

Any remaining questions you have about the workshops or about cervical cancer?

Survey End

Section C

Will you get screening for cervical cancer in the near future (within the next year)?

- Yes
- Maybe
- No

Do you have any concerns with getting screening for cervical cancer?

[figure not shown]
Where would you go to get cervical cancer screening?

- My usual doctor or other clinician
- The health department
- Will return to the community center
- Another health care provider (not yet found)
- Not sure yet

Section C (continued)

In the workshop you attended today, we did not discuss self-collection as an option.

If self-collection was an option, would you have preferred this method?

Yes

Maybe

No

→ Any remaining questions you have about the workshops or about cervical cancer? **Survey End**

At this time - please provide a quick 1 on 1 instruction on self-collection for cervical cancer screening.

After the participant is done, please return to complete the remainder of this survey.

Patient agreed and collected a self sample → Skips to to Section E

Patient declined a self sample today

→ Any remaining questions you have about the workshops or about cervical cancer? **Survey End**

Section D

Did the participant get screening for cervical cancer today? (Self Collected)

Yes, clinician collection → Skips to to Section F

Yes, self-collection → Skips to to Section E

No → Skips to to Section G

Section F

How comfortable did you feel with this method?

Extremely comfortable

Somewhat comfortable

Neither comfortable nor uncomfortable

Somewhat uncomfortable

Extremely uncomfortable

How likely would you get screening for cervical cancer again?

Extremely likely

Somewhat likely

Neither likely nor unlikely

Somewhat unlikely

Extremely unlikely

Any remaining questions you have about the workshops or about cervical cancer?

Survey End

Section E

How comfortable did you feel with this method?

- Extremely uncomfortable
- Somewhat uncomfortable
- Neither comfortable nor uncomfortable
- Somewhat comfortable
- Extremely comfortable

How likely would you do self-collection for cervical cancer screening again?

- Extremely unlikely
- Somewhat unlikely
- Neither likely nor unlikely
- Somewhat likely
- Extremely likely

Would you have preferred a clinician to help with the collection?

- Do not prefer
- Prefer slightly
- Prefer a moderate amount
- Prefer a lot
- Prefer a great deal

Did you have any confusion with the instructions?

- No
- Yes

How likely are you to recommend this method to others?

- Extremely unlikely
- Somewhat unlikely
- Neither likely nor unlikely
- Somewhat likely
- Extremely likely

Any remaining questions you have about the workshops or about cervical cancer?

Survey End

Section G

Will you get screening for cervical cancer in the near future (within the next year)?

- Yes
- Maybe
- No

Do you have any concerns with getting screening for cervical cancer?

Where would you go to get cervical cancer screening?

- My usual doctor or other clinician
- The health department
- Will return to the community center
- Another health care provider (not yet found)
- Not sure yet

Any remaining questions you have about the workshops or about cervical cancer?

Survey End

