20.3.2 Secondary Outcome Measures and Analysis

Qualitative survey data will be obtained through pre- and post-workshop surveys to evaluate the impact of the educational workshops.

Further statistical support for this program will be obtained through consultation with statisticians in the UW-Madison SMPH and/or UW Carbone Cancer Center Biostatistics Shared Resource. For quantitative data, differences will be tested with Wilcoxon Rank-Sum tests for continuous or ordinal categorical data, Chi-Squared tests for unordered categorical data, and binomial tests for dichotomous data.

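### In the Appendix C survey, the answer options for comfort and repeat likelihood run in opposite directions for self-collection and clinician collection, so option order is fully confounded with method on these two items

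*Combined protocol and SAP*

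**What the plan says.** Appendix C routes each woman to a section by the collection method she used.

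- Control women screened by a clinician answer Section B.
- In the intervention workshops the branches are "Yes, clinician collection → Skips to to Section F" and "Yes, self-collection → Skips to to Section E".
- A control woman who first declines and later self-collects is also sent to Section E: "Patient agreed and collected a self sample → Skips to to Section E".

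Sections B, E and F share the comfort stem, "How comfortable did you feel with this method". Each also has a repeat-likelihood item. In B and F it reads "How likely would you get screening for cervical cancer again", and in E it reads "How likely would you do self-collection for cervical cancer screening again".

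Protocol 13.1.3.2 names comfort with either collection method as a survey theme. It says that the community health workers give the survey verbally, that answers are recorded in Qualtrics, and that they are not linked to the study ID. Section 20.3.2 assigns "Wilcoxon Rank-Sum tests for continuous or ordinal categorical data" to quantitative data. No numeric code, recoding rule or randomisation of options is stated.

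**The concern.** The direction of the option list changes exactly where the method being rated changes. Both clinician-collection sections start from the favourable end. The self-collection section starts from the unfavourable end, with "Extremely uncomfortable" as its first comfort option.

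In a verbally administered survey, the order in which answers are presented can shift what people choose. Any such shift would fall entirely on the contrast between methods. It could not be removed at analysis, because no woman rates self-collection in the B/F order or clinician collection in the E order.

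A second risk is mechanical. If numeric codes followed list position, a rank-sum test would compare two scales pointing in opposite directions. At stake is any statement that women found one method more comfortable than the other, or would more readily repeat it.

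**Working it through.** **Step 1: set the sections side by side.** All entries are from Appendix C.

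| Item | B (control, clinician) | F (intervention, clinician) | E (self-collection, both arms) |
|---|---|---|---|
| Comfort: first option | extremely comfortable | extremely comfortable | extremely uncomfortable |
| Comfort: last option | extremely uncomfortable | extremely uncomfortable | extremely comfortable |
| Repeat: first option | extremely likely | extremely likely | extremely unlikely |
| Repeat: last option | extremely unlikely | extremely unlikely | extremely likely |
| Repeat: what the stem asks about | screening in general | screening in general | self-collection |

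B and F agree with each other, and E is reversed on both items (2 of 2). Section E's item on recommending the method also runs from unlikely to likely. The pattern is therefore consistent and does not look like a fault of text extraction. The live Qualtrics form could not be checked.

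**Step 2: check the confounding.** Self-collectors in either arm reach E, and clinician-collected women reach B or F. Method and option order coincide in every cell, so neither adjustment nor a subgroup analysis can separate them.

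**Step 3: list-position coding (conditional).** The documents give no figure to reproduce. Suppose options were coded 1 to 5 in displayed order. An option at position k in B or F sits at position 6 − k in E, so the shift is 6 − 2k:

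- most comfortable answer: 1 against 5, a shift of 4;
- second most comfortable: 2 against 4, a shift of 2;
- neutral: 3 against 3, a shift of 0.

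The effect on a rank-sum test was simulated with the same true comfort under both methods (2000 runs, two-sided 0.05). The distributions, from most to least comfortable, and the 40, 80 or 100 women per method are assumptions.

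| Assumed distribution (%) | Mean, E against B/F, list-position codes | False rejection, list-position codes | False rejection, label codes |
|---|---|---|---|
| 40/30/15/10/5 | 3.9 against 2.1 | 100% at each size | 4% to 5% |
| 25/25/25/15/10 | 3.4 against 2.6 | 77%, 97%, 99% | about 5% |
| 10/20/40/20/10 | 3.0 against 3.0 | 5% to 6% | 4% to 5% |

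For the first row, the E mean is 5(0.40) + 4(0.30) + 3(0.15) + 2(0.10) + 1(0.05) = 3.9, and the B/F mean is 6 − 3.9 = 2.1. Coding by label removes this artefact completely.

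**Step 4: the order effect, which label coding does not remove.** As an illustration, take the 40/30/15/10/5 distribution, code by label with 5 as most comfortable, and assume that the last option listed draws 2.5% of respondents away from the second most comfortable answer.

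- Self-collection: 3.9 + 0.025 × (5 − 4) = 3.925.
- Clinician collection: 3.9 + 0.025 × (1 − 4) = 3.825.
- Spurious gap: 0.10. If 5% moved, the means would be 3.95 and 3.75, a gap of 0.20.

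If the first option drew them instead, the gap would have the same size and the opposite sign. The documents support neither the share moved nor the direction.

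**The case against.** The best reply is that no listed endpoint needs this contrast. Section 2 defines satisfaction as satisfaction with the workshops, assessed qualitatively, and willingness as willingness to use self-collection, which Section E can describe in one group. Comfort by method is a survey theme in 13.1.3.2, and 20.3.2 names the rank-sum test generally without specifying B or F against E. This stands, and it limits the point to comparisons of methods on two items. A reader might infer that the secondary endpoints as a whole are compromised, but the documents do not support that.

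A reader might also infer that the analysis will run on reversed scales. Every option carries a full verbal label and no position coding is planned. The rejection rates above show what a coding mistake would do, not that one is intended, and they fall to the nominal level when answers are symmetric.

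On the order effect, it is fair to say that verbal administration does not prove that options are recited in printed order, and some sessions run through a translator. That leaves the effect uncertain but does not rule it out.

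A further inference would be that the preference items should also be put on one format. They ask different questions: Sections B and C ask whether self-collection would have been preferred, and Section E asks whether a clinician's help would have been. No comparison between them is planned. The Yes/Maybe/No item is also tied to the control-arm offer of self-collection described in Section 11, so a change of format could disturb that trigger.

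Finally, women reach B, E or F by accepting a method, so the contrast is self-selected whatever the option order. That is true, but it is no reason to add a second, avoidable bias.

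**Conclusion.** The point holds for two items. On comfort and repeat likelihood, option order is fully confounded with collection method, and a comparison between methods would mix the two. The repeat-likelihood item has a further defect: its stems ask about different things, so it would not be comparable even with a common order.

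The order effect has unknown size and direction. The reversed-scale artefact, up to 4 points per answer on a five-point scale, arises only if codes follow list position and are never realigned. The conclusion assumes that the Qualtrics form matches the printed Appendix C.

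This is a minor but worthwhile correction. Coding can be repaired after the data are in, whereas an order effect in the collected answers cannot. Because answers are not linked to the study ID, they cannot later be checked against other participant records.

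**What to change.** 1. Use one option order for the comfort and repeat-likelihood items in Sections B, E and F. Either direction works. Negative-first would match Section A and the item on recommending the method in Section E.
2. Give the repeat-likelihood item a matched stem in all three sections, for example by asking in each about repeating screening by the method just used.
3. State in 20.3.2 that these items are coded by label, in the same direction for every section.
4. Leave the preference items unchanged.

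The cost is a small survey edit and any IRB amendment it needs, since the signatory commits to the approved protocol. The documents do not show whether workshops have begun. If they have, align the codes by label before analysis and report the difference in option order and stem as a limitation of any comparison between methods.

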13.1.3.2 UW Health Post-Workshop Satisfaction Survey (UW-PSS)

Additional survey questions will be administered verbally by CHWs and answers recorded in Qualtrics for data collection. Responses will not be linked to the study ID or other identifiable information. Theme of survey questions is below (full survey in Appendix C):

- Comfort with method (either self-collection or clinician-collection)
- How likely would the participant get screening for cervical cancer again?
- If self-collection (or clinician-collection) was an option, would they have preferred this method.

- If not getting screening today, will they go for screening in the near future?
 - o If not why? Where?
- Understanding of instructions (self-collection)

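### Two UW-PSS items, repeat intention and preference, are asked differently by screening method and depart from the themes in Section 13.1.3.2, so a tested difference on either could come from wording alone.

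*Combined protocol and SAP*

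**What the plan says.** Section 13.1.3.2 lists the UW-PSS themes. One is repeat intention, given without reference to method: "How likely would the participant get screening for cervical cancer again". Another is preference, given in mirrored form: "If self-collection (or clinician-collection) was an option, would they have preferred this method".

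Appendix C holds the survey itself, with skip routing. Control women screened by a clinician go to survey Section B, and intervention women screened by a clinician go to Section F. Both sections ask "How likely would you get screening for cervical cancer again". Women who self-collect go to Section E, which asks "How likely would you do self-collection for cervical cancer screening again".

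On preference, Sections B and C ask control women "If self-collection was an option, would you have preferred this method", answered Yes, Maybe or No. Section E asks "Would you have preferred a clinician to help with the collection", answered on five steps that end at "Prefer a great deal". Sections F and G have no preference item.

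On analysis, Section 20.3.2 says: "For quantitative data, differences will be tested with Wilcoxon Rank-Sum tests for continuous or ordinal categorical data". It adds chi-squared tests for unordered categories and binomial tests for dichotomous data. It does not say which survey items are tested or which groups are compared.

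**The concern.** The wording a woman hears depends on how she was screened, so on these two items question and method cannot be separated. A self-collector who is certain to be screened again, but would see a clinician next time, answers low in Section E. A clinician-screened woman who is equally certain, but would self-collect next time, answers high in B or F. The two have the same intention to be screened, yet their scores differ.

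The preference answers share no scale. They differ in the method asked about, in direction and in number of levels, and wanting a clinician's help is not the same as wanting clinician collection.

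What is at stake is a secondary endpoint. Section 2 includes willingness to use self-collection, or preference for it, assessed by survey. The loss cannot be made good later: Sections 13.1.3.2 and 16.2 say that UW-PSS responses are not linked to the study ID, so an answer that was never asked for cannot be recovered for an individual woman.

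**Working it through.** The plan gives no figure on this point, so the check is an item-by-item comparison across the survey sections of Appendix C.

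| Item | B: control, clinician-screened | C: control, not clinician-screened | E: self-collected | F: intervention, clinician-screened | G: intervention, unscreened |
|---|---|---|---|---|---|
| Comfort | asked | – | same wording, options in reverse order | same wording | – |
| Repeat intention | any method | – | self-collection only | any method | – |
| Preference | self-collection, 3 levels | self-collection, 3 levels | clinician help, 5 levels | none | none |
| Next-year screening, concerns, place | – | asked | – | – | same wording |

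The four Section A items are the same for every woman. Only the second and third rows of the table compare unlike questions. Set against Section 13.1.3.2, Section E does not carry the neutral repeat theme, and neither E nor F carries the mirrored preference theme as described.

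Routing matters too. A control woman who accepts the self-collection offer in Section C is sent on to Section E. Section E therefore mixes intervention self-collectors with control crossovers, and any contrast of B/F with E is by method used.

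**Size, illustration 1 (assumed inputs).** Let a be the share in each group who would be screened again by some method, and s the share of those self-collectors who would switch method. The B/F item shows a, the Section E item shows a(1 − s), and the false gap is a × s.

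- a = 0.90, s = 0.20: Section E shows 0.90 × 0.80 = 0.72 against 0.90, a gap of 18 points.
- a = 0.90, s = 0.05: gap 0.90 × 0.05 = 4.5 points.
- a = 0.90, s = 0.30: gap 0.90 × 0.30 = 27 points.

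**Size, illustration 2 (assumed inputs).** Two-sided 0.05 rank-sum tests on two five-level items were simulated 3,000 times per setting. The neutral item has probabilities 0.03, 0.05, 0.12, 0.30, 0.50 from least to most likely. The method-specific item has the same distribution, a mild shift (0.05, 0.08, 0.15, 0.32, 0.40) or a moderate shift (0.08, 0.12, 0.20, 0.30, 0.30). Intention to be screened by any method is taken as equal in both groups throughout. The proportion of trials that reject is:

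| Method-specific item | 60 per group | 80 per group | 100 per group |
|---|---|---|---|
| Same distribution | 0.048 | 0.047 | 0.054 |
| Mild shift | 0.239 | 0.287 | 0.366 |
| Moderate shift | 0.765 | 0.877 | 0.942 |

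The first row is close to the nominal 5%. The other two show how often wording alone would give a significant result under these assumptions.

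**The case against.** The strongest reply is that no comparison of these items is planned. Section 20.3.2 matches tests to data types and names no item and no pair of groups. A reader might infer that the protocol commits to testing B/F against E, or one arm against the other, on these two items. The text does not say so. The point therefore has to be conditional on the generic tests being applied to them.

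Second, Section E's wording has a purpose. Asking self-collectors whether they would self-collect again directly measures the willingness endpoint in Section 2. That stands, and the item should be kept. What is missing beside it is the neutral item.

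Third, Section 13.1.3.2 lists themes and refers to Appendix C for the full survey, so it does not promise identical wording. This is fair, but the themes it lists are neutral and mirrored, and Section E is neither.

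Fourth, some asymmetry in preference follows from the design. Control women were not taught self-collection and must answer hypothetically, while women in Section F have already chosen a clinician. This explains different lead-ins. It does not require different targets and scales.

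Fifth, identical wording would not make B/F against E a randomised comparison, because the women are grouped by the method they used. This stands in full and limits what any rewording can deliver.

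**Conclusion.** The point holds for two items, repeat intention and preference. If Section 20.3.2's tests are applied to them across screening methods, a difference could come from wording alone. On repeat intention, the bias would run against self-collection wherever self-collectors are less sure of repeating the method than of being screened again.

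A reader might infer that the survey comparisons as a whole are between different questions. They are not: the comfort, Section A and next-year items are worded alike, and the screening-today outcome does not depend on the two affected items. The reversed order of options for comfort in Section E is a separate coding matter.

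The 18-point gap and the rejection rates are not estimates for this trial. They rest entirely on the assumed shares and distributions shown, and the documents give nothing from which to replace them. What the documents do establish is the mismatch in wording and scale, the absence of a preference item in F and G, and the silence of Section 20.3.2 on which items and groups are compared. This is a limited defect in secondary survey data, but it is cheap to correct and cannot be repaired once the answers have been collected.

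**What to change.** In Appendix C:

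- Add to Section E the item already used in B and F, "How likely would you get screening for cervical cancer again". Keep the self-collection-again item for the willingness endpoint.
- Add to B and F a matching item on how likely the woman is to use the same method again.
- Add one common preference item (self-collection, clinician collection, no preference) to Sections B, C, E, F and G. Control women who pass from C to E would meet it twice, so state at which point it is recorded.
- Keep the existing Section C question that leads to the self-collection offer. Section 11 ties that offer to a control woman's answer, so replacing the question outright would disturb the offer.

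In Section 20.3.2, name the items and groups to be compared and restrict tests to identically worded items. Label contrasts of Sections B/F with E as by method used and not randomised, and report the remaining unlike items descriptively within method.

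The cost is re-translation of two or three items, the skip-logic edits, and under a minute of interview time.
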